#### Title:

A Histomorphometric Analysis of Bone Formation following sinus augmentation with Two Different Bone Graft Materials. A pilot study in humans.

#### Introduction:

Sinus augmentation procedure is a well-accepted and predictable surgical procedure that is used to increase the bone volume to facilitate implant placement for individuals who otherwise present with inadequate bone quantity in the posterior maxilla. In 1980, Bovne and James published a technique for maxillary sinus augmentation using autogenous bone. Since then, several different techniques have been developed and are currently being utilized 6-9 for sinus augmentation. The original sinus augmentation protocol utilized autogenous bone 5.10 from either intraoral or extra oral sources. The disadvantages of utilizing autogenous bone are requirement of an additional surgical procedure, increase in surgical time and post-surgical morbidity. Moreover, autogenous bone has reported high and unpredictable resorption 11,12 rate. Therefore, various grafting materials such as allografts, xenografts, alloplastic ma-1.13-18 terials, and mixtures of various materials have been utilized in sinus floor elevation. Del Fabbro et al. concluded in their systematic review that bone-substitute materials are as effec-

2

tive as autogenous bone when used alone or in combination with autogenous bone.

Anorganic bovine bone mineral (Bio-Oss, Geistlich, Princeton, NJ) (ABBM) is a bone substitute that is manufactured from bovine bone mineral having a microscopic structure similar to human cancellous bone. In humans, ABBM alone or mixed with other materials was found to be highly osteoconductive and provided a scaffold for new

4

bone formation in extraction sockets or sinus augmentations. The results of sinus aug-14-24 mentations with xenografts are complete and well documented. Jensen T et al. reported that there is no statistical difference between the use of ABBM alone and a mixture with autogenous bone as graft material for maxillary sinus augmentation.

Inteross (Sigma Graft) is another anorganic bovine bone mineral bone substitute that is manufactured from bovine bone and is supposed to have a similar microscopic structure to Bio-oss but with more surface area. This will be an attempt to compare the clinical performance with histomorphometric analysis of the bone that is formed using the two different graft materials.

#### **Objective:**

The purpose of this investigation is to compare new bone formation by means of histomorphometric analysis following maxillary sinus augmentation using two different bone graft materials.

#### **Null Hypothesis:**

There is no histomorphometric difference in new bone formation in maxillary sinuses augmented using two different materials, ABBM (Bio-oss) and ABBM (InterOss).

5

#### Material & Methods:

#### **Patient selection:**

20 patients who require sinus augmentation prior to implant placement in the posterior maxilla at Loma Linda University School of Dentistry (LLUSD), Advanced Education Program in Implant Dentistry will be selected to participate in this study. Patient will complete a medical history form and be selected using the following inclusion and exclusion criteria.

#### **Inclusion Criteria:**

- 1. Over 18 years old who are able to read and sign an informed consent form.
- 2. Patient who has good oral hygiene (Full-mouth plaque score <25%).
- 3. Subject would be available for study monitoring and follow-up visits.
- 4. Patients with missing teeth in the maxillary posterior region who will require sinus augmentation for implant placement. The patients may be partially or completely edentulous.
- 5. Patient is a candidate for delayed implant placement approximately 8 months following sinus grafting.
- Patient will be evaluated for the dimensions of the maxillary sinus after initial CBCT evaluation and patient with the following minimum dimensions will be included. Length (anterior-posteriorly) – 25mm

Width (medial-laterally) - 18mm

Height (coronally-apically) – 25mm

#### **Exclusion Criteria:**

A medical history that will complicate the outcome of the study such as

- 1. Alcohol, drug dependency.
- 2. Signs or symptoms of chronic maxillary sinus disease.
- 3. Current smoker.
- 4. History of head and neck radiation treatment.
- 5. Poor health, conditions like uncontrolled diabetes, uncontrolled hypertension or other uncontrolled systemic disease.
- 6. Physical or psychological reason that might affect the surgical procedure or the subsequent prosthodontic treatment and/or required follow-up examinations.
- 7. Also, subjects who are nursing or pregnant will be excluded from the study.

A guideline and treatment protocol for patient care will be submitted to the Institutional Review Board (IRB) of Loma Linda University (LLU) and the research review committee for approval. All clinical procedures will be performed at the Center for Implant Dentistry, Loma Linda University School of Dentistry.

#### **Informed Consent:**

In accordance with the standards of conduct established by the Institutional Review Board of Loma Linda University, participants will be required to sign an informed consent. The purpose and the nature of the study will be explained to the subjects by one investigator (SU) and patient who will meet our inclusion criteria will then be invited to participate. Subjects will be required to read, understand, and sign the consent form before being enrolled in the study. Hard copy will be retained following the standard protocol set by the Institutional Review Board of Loma Linda University. Randomization – Quickcalcs software from Graphpad (Graphpad software Inc, La Jolla, CA USA) will be used to randomly assign patients. All patients will undergo sinus augmentation and will be randomly placed into two groups according to the graft material to be used in the surgical procedure. If a patient requires bilateral sinus augmentation, (two sinus on either side in the same patient) each sinus will be considered as one unit for the randomization procedure.

Group A: 10 Maxillary sinus augmentation using ABBM (InterOss).

Group B: 10 Maxillary sinus augmentation using ABBM (Bio-Oss).

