#### **Biopsy Procedure:**

- After 8 months of healing, a full-thickness flap will be reflected and previous antrostomy site will be located using the same surgical template. Two trephines (2.75mm internal diameter and 3.5mm external diameter, ACE Surgical Supply Company, Inc., Brockton, MA) will be used to collect at least 8mm length biopsy specimen. Two cores will be taken from each patient site; one core from the previous lateral window of each sinus augmentation site without interfering with implant placement and one core from the implant osteotomy site. When obtaining the core from the implant osteotomy site, at least 8mm in length of the grafted bone will be included in the core. The trephines are marked at 8mm,10mm,13mm,15mm. The core samples will be kept in the trephine in 10% buffered formalin, coded and mailed to the laboratory for the histomorphometric analysis.
- 2. The alveolar ridge will be prepared for implant placement, in accordance with the conventional surgical protocol, and implants of appropriate dimensions will be placed.

Immediately after insertion the stability of the implants will be recorded by measuring the ISQ values.

- 3. Post-operative care instructions will be provided as described previously.
- 4. Appropriate healing time for the implants will be allowed for osseointegration, and definitive restorative prostheses will be constructed accordingly.

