#### Histology / MicroCT assessment

The trephine with the retrieved specimens will be placed in 10% neutral buffered formalin. Each specimen will be labeled and packaged in an individual container, which will then be numerically coded to keep the patient's information confidential and examiners will be blinded. Specimens (40) will be sent to the Hard Tissue Research Laboratory, University of Minnesota School of Dentistry for histomorphometric analysis. Or the specimens will be analysed by using a MicroCT at the university of Loma Linda, center for radiation research. The microCT will give us digital reconstruction of the 3D structure of the core material. This will be analysed for new bone formation, amount of graft material remaining, interaction between the graft and the patient's native bone.

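### If bilateral patients enrol, randomising each sinus separately gives both sides the same material about half the time and forgoes a within-patient comparison

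*Combined protocol and SAP*

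**What the plan says.** The randomisation text sits in the Informed Consent section. It first says that "Quickcalcs software from Graphpad (Graphpad software Inc, La Jolla, CA USA) will be used to randomly assign patients", which describes assignment by patient. It then adds a rule for one kind of patient: "If a patient requires bilateral sinus augmentation", then "each sinus will be considered as one unit for the randomization procedure". Ten augmentations are planned with each material. No section requires the two sides of one patient to differ, and no blocking or pairing is described.

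The Pre-operative procedure section again speaks of assigning patients, not sinuses, to Group A or B. The Statistical analysis section names ANCOVA and mentions neither pairing nor within-patient correlation.

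Three other statements bear on how many bilateral patients are expected. Patient selection plans "20 patients who require sinus augmentation prior to implant placement in the posterior maxilla". The Biopsy Procedure section says "Two cores will be taken from each patient site". The Histology / MicroCT section says "Specimens (40) will be sent to the Hard Tissue Research Laboratory".

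**The concern.** Two sinuses of one person share that person's age, health and healing capacity. If each receives a different material, these shared influences cancel in the comparison. If both receive the same material, the patient gives two correlated results to one arm and none to the other.

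The rule as written leaves this to chance. With about ten sinuses per arm, variation between patients may be a large part of the noise, so precision that can be had without recruiting anyone is worth taking. What is at stake is precision and protection against chance imbalance, not validity.

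**Working it through.** **Inputs from the documents.** 20 patients (Patient selection); 10 + 10 augmentations, with the sinus as the unit in bilateral patients (Informed Consent); 2 cores per site (Biopsy Procedure); 40 specimens (Histology / MicroCT assessment). The plan states no variance, effect size or power, so there is no figure of its own to reproduce.

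**Assumptions.** Number of bilateral patients b = 2 to 5; correlation between the two sinuses of a patient ρ = 0.3 to 0.7; 20 sinuses in all, one value per sinus, variance σ² = 1.

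**Step 1: chance of the same material on both sides.** On a fixed list of 10 + 10, once the first sinus is assigned, 9 of the remaining 19 places carry the same material: 9/19 = 47.4%. With independent 1:1 draws it is 50%. Equal splits of 22 to 40 sinuses give 47.6% to 48.7%. On the 10 + 10 list, the chance that at least one bilateral patient receives one material on both sides is about 72%, 85% and 96% for b = 2, 3 and 5.

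**Step 2: variance of the difference in arm means.** Twenty unrelated sinuses give 1/10 + 1/10 = 0.200. Each split pair changes this by −2ρ/100, and each same-material pair by +2ρ/100. Hence:

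- all pairs split: 0.2 − 2bρ/100
- expected under sinus-level allocation: 0.2 − (10/19 − 9/19) × 2bρ/100 = 0.2 − (1/19) × 2bρ/100
- every pair on one material: 0.2 + 2bρ/100

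| b | ρ | Split | Expected as planned | Reduction |
|---|---|---|---|---|
| 2 | 0.3 | 0.188 | 0.199 | 6% |
| 3 | 0.5 | 0.170 | 0.198 | 14% |
| 5 | 0.5 | 0.150 | 0.197 | 24% |
| 5 | 0.7 | 0.130 | 0.196 | 34% |

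For b = 5 and ρ = 0.5 the standard error is 13% smaller, since √(0.150/0.197) = 0.87.

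**Step 3: does the gain survive an analysis that models the patient?** Generalised least squares with ρ known, averaging the planned allocation over 4,000 random lists:

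| b | ρ | As planned | Split | Reduction |
|---|---|---|---|---|
| 2 | 0.3 | 0.196 | 0.184 | 6% |
| 2 | 0.5 | 0.188 | 0.167 | 11% |
| 5 | 0.5 | 0.172 | 0.133 | 22% |
| 5 | 0.7 | 0.139 | 0.092 | 33% |

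The range is almost the same, so the gain does not come from using a crude comparison.

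**Step 4: do the planned counts contain any bilateral patients?** 20 sites × 2 cores = 40 specimens, and 10 + 10 = 20 sinuses. Twenty patients with 20 sinuses is one sinus each, so b = 0. With b bilateral patients, either only 20 − b patients are needed or 20 + b sinuses are treated. The counts and the bilateral rule do not fit together as written.

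**The case against.** The strongest reply is that on the plan's own counts the effect is zero: 20 patients, 20 sinuses and 40 specimens leave no room for a bilateral patient, and the protocol provides for such patients without forecasting any. This stands as a limit on size. It does not remove the point, because the protocol writes an explicit rule for bilateral cases and admits completely edentulous patients, in whom bilateral need is plausible.

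A reader might infer that the planned allocation harms or biases the comparison. It does not. Sinus-level randomisation is unbiased, and its expected variance (0.198 for b = 3, ρ = 0.5) is about the same as that of 20 unrelated patients (0.200). What is lost is a possible gain. The unfavourable case, in which every pair receives one material on both sides, gives 0.230 for b = 3 and 0.250 for b = 5 at ρ = 0.5. On a 10 + 10 list its probability is only about 10.8% and 2.5%, so it should not be read as the expected result.

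A reader might also think the change costs nothing. It needs no extra patients or procedures, but some recorded complications, such as pain or nasal leakage, may be hard to assign to a side. The full benefit also requires an analysis that the plan lacks. If split pairs were analysed by ANCOVA as independent, the true variance would fall but the reported standard error would not show it, and intervals would be wider than needed. With so few pairs the patient variance is poorly estimated, and the figures in Step 3 treat ρ as known.

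Finally, the patient-level wording in two sections competes with the sinus rule. If it governed, both sides would always match, which would strengthen the point.

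**Conclusion.** The point holds as a cheap improvement to the design, conditional on bilateral patients enrolling. The chance that such a patient receives one material on both sides is 47% to 50%, depending on how the list is built, which the protocol does not describe. Assigning one material to each side would lower the variance of the arm difference by about 6% to 34%, and by nothing if no bilateral patient enrols. That range rests on assumed values (2 to 5 bilateral patients, ρ of 0.3 to 0.7) that the documents neither give nor rule out.

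The trial suits the change. The cores come from each grafted sinus, one surgeon uses one technique, and the specimens are read blinded. The CBCT evaluation should show bilateral need in time to use a side list. The documents do not support a claim of bias, or of a loss that is certain to occur.

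**What to change.** In the Informed Consent section, replace the last sentence of the randomisation text with:

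> In a patient who requires bilateral augmentation, the side (right or left) that receives InterOss is randomised and the other side receives Bio-Oss; unilateral patients are randomised 1:1 in blocks so that the totals stay at or near 10 + 10.

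The blocking matters because the number of bilateral patients is not known in advance, and a right/left list alone does not keep the arms balanced.

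In the Statistical analysis section, state that sinuses are analysed with a linear mixed model with a random patient effect, fixed effects for material and the planned covariates, and small-sample degrees of freedom. State also that a bilateral patient with only one evaluable sinus contributes that sinus as a single observation.

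Reconcile the counts of patients, sinuses and specimens (Patient selection, Informed Consent, Histology / MicroCT assessment) with the bilateral rule. Do the same for the patient-level assignment wording in the Informed Consent and Pre-operative procedure sections.

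The cost is a few sentences, a short right/left list and a blocked list for unilateral patients. No additional patients or procedures are needed. The downsides are that complications which cannot be attributed to a side cannot be compared by arm in bilateral patients, and that with few pairs the patient variance is imprecise.

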#### **Pre-operative procedure**

- At a pre-surgical appointment, the patient's vital signs (blood pressure, pulse rate) will be recorded and the patient's medical history will be updated. At this point, patients will be randomly assigned to Group A or B.
- 2. Patients will be given the following three choices of anesthesia for the sinus surgery:
  - a) Local anesthesia (LA) only.
  - b) LA in conjunction with oral sedation (Halcion 0.25mg, Roxane Laboratories Inc., Columbus, OH). Administered 30 minutes before the appointment.

c) LA in conjunction with intravenous (IV) sedation.

A patient who chooses IV sedation will have a pre-surgical interview with the anesthesiologist (Surgery Center for Dentistry, Loma Linda University School of Dentistry) who will conduct sedation at the time of the surgery.

- 3. All patients will be questioned regarding drug allergy and prescribed with appropriate antibiotics (Amoxicillin 500 mg or Clindamycin 300mg, TID for 10 days, to start day 1 before the day of surgery) analgesic (Ibuprofen 800 mg) to take 1 tab 1 hour before the surgery and for post-operative usage as needed for pain. The patient will also be instructed to rinse with 0.12% chlorhexidine gluconate solution (Peridex, Zila Pharmaceuticals Inc., Phoenix, AZ) twice a day starting 1 week before the surgery to continue for 2 weeks after the surgery.
- 4. The radiographic template will be converted into a surgical template. The proposed implant locations in the radiographic template will be finalized and modified if necessary after reviewing the CBCT scan with the template in place. The location of the anterior wall of the sinus cavity will be marked on the surgical template.
- 5. All pre-operative and postoperative instructions will be given to the patient in an oral and written format. All of the patient's questions about the instructions will be answered.

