#### Patient Withdrawal and/or Replacement:

If a subject decides to withdraw from the study prior to sinus augmentation, this individual will be replaced with another subject. If a perforation of the sinus membrane (> 5 mm) occurs during the surgical procedure, the site will be closed and the augmentation procedure will be aborted. This individual will be replaced with another subject.

If a subject is withdrawn from the study following sinus augmentation, all data associated with this individual will be reported but not included in the final results and analysis. If the subject is unable to attend the required post-operative sessions or is uncooperative, this individual may be dismissed from the study.

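### Bilateral patients are randomised by sinus in one section and by patient in another, and the planned counts agree only if no patient is bilateral

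*Combined protocol and SAP*

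**What the plan says.** **Randomisation unit.** The Informed Consent section says that the software "will be used to randomly assign patients". For a patient who needs both sides grafted it then says that "each sinus will be considered as one unit for the randomization procedure". The Pre-operative procedure, which sets the time of allocation, says that "patients will be randomly assigned to Group A or B" and makes no mention of bilateral cases. Patient Withdrawal and/or Replacement says that "this individual will be replaced with another subject", both for withdrawal before grafting and for a large membrane perforation.

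**Counts.** Patient selection plans for "20 patients who require sinus augmentation prior to implant placement". Informed Consent sets each group at 10 sinus augmentations. The Biopsy Procedure takes two cores per site, and Histology / MicroCT assessment states "Specimens (40) will be sent".

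**Analysis.** Statistical analysis names an ANCOVA with unspecified covariates and no patient effect. Histomorphometric analysis averages two slides within a core. No section says how to combine the two cores of a sinus or the two sinuses of a patient.

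Bilateral cases are expected: Informed Consent provides for them, the inclusion criteria admit completely edentulous patients, and no exclusion criterion rules them out.

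**The concern.** A reader cannot tell when enrolment is complete, because a target of 20 patients and a target of 20 sinuses part company with the first bilateral patient. Nor does the plan say how the second side is assigned: drawn independently, matched to the first, or given the other material. These choices lead to different error rates for the same simple test and to different precision. They have to be settled before the allocation list is made. The comparison of the two materials is the study's only stated objective and is tested at P < .05, so the pilot label does not make the matter harmless.

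**Working it through.** **1. Counts.** Inputs: 20 patients (Patient selection), 10 + 10 sinuses (Informed Consent), two cores per site (Biopsy Procedure). The plan's figure reproduces with one sinus per patient: 20 × 1 × 2 = 40 cores. With b bilateral patients, 20 patients give 20 + b sinuses and 2(20 + b) = 40 + 2b cores. If sinuses are held at 20, cores stay at 40 and patients fall to 20 − b.

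| b | 20 patients kept: sinuses, cores | 20 sinuses kept: patients, cores |
|---|---|---|
| 0 | 20, 40 | 20, 40 |
| 2 | 22, 44 | 18, 40 |
| 5 | 25, 50 | 15, 40 |
| 10 | 30, 60 | 10, 40 |

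All the stated counts hold together only at b = 0.

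**2. The second side under the sinus rule.** From a balanced list of 10 + 10, once one side is drawn, 9 of the remaining 19 entries carry the same material: 9/19 = 47%. The two sides differ with probability 10/19 = 53%.

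**3. Type I error.** Simulation of a two-sided 5% t-test on 20 sinus values, ignoring the patient, with 40,000 runs per setting. The within-patient correlation of 0.5 and the values of b are assumptions.

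| b | Sinuses drawn independently | Both sides follow the patient | Opposite materials per side |
|---|---|---|---|
| 2 | 4.8% | 6.4% | 3.8% |
| 4 | 5.0% | 7.4% | 3.0% |
| 6 | 4.9% | 8.8% | 2.3% |
| 10 | 5.0% | 11.5% | 0.9% |

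Over correlations of 0.3 to 0.7 and the same values of b, the ranges are 4.8% to 5.2%, 5.8% to 14.5%, and 4.4% down to 0.2%.

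**4. Precision.** With 10 sinuses per material, sinus SD of 1 and correlation ρ, the variance of the difference in means is 0.2 + 0.02 × ρ × b × c. Here c is +1 if both sides match, −1 if they are opposite, and on average 9/19 − 10/19 = −1/19 for independent draws from the balanced list. With ρ = 0.5:

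- b = 6, independent: 0.2 − 0.06/19 = 0.197, SE 0.44 SD.
- b = 6, opposite: 0.2 − 0.06 = 0.14, SE 0.37 SD, which is 29% less variance (1 − 0.14/0.197).
- b = 6, both follow the patient: 0.2 + 0.06 = 0.26, SE 0.51 SD.
- b = 4, independent: 0.2 − 0.04/19 = 0.198, SE 0.445 SD; opposite: 0.16, SE 0.40 SD.

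This also explains step 3: a t-test that ignores the patient estimates a variance near 0.2 under every allocation, while the true value is above or below it.

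**The case against.** The best defence is that Informed Consent does give a rule. The sinus sentence reads naturally as an exception, for bilateral patients, to the general statement about assigning patients. The Pre-operative sentence can then be read as fixing only the time of allocation. On that reading, with independent draws, a sinus-level test holds its 5% level. If sinuses are capped at 20, the 10 + 10 groups and the 40 cores agree for any b, and only the figure of 20 patients has to move. Opposite materials per side is a design option, and a pilot without a power claim is not wrong to omit it.

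Most of this stands, and it rules out several stronger readings that a reader might infer:

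- **That sample size and error term are undefined.** They are ambiguous between identifiable readings.
- **That the plan as written inflates type I error.** Inflation needs both sides to follow the patient's assignment, which the sinus sentence argues against.
- **That the within-patient comparison is wasted.** About 53% of bilateral patients would still receive both materials. With b = 6 and a known correlation of 0.5, a patient effect would bring the SE from about 0.44 to 0.41 SD under the existing sinus rule (about 0.35 SD with opposite sides).
- **That the replacement rule discards or double-counts a sound second sinus.** The documents are silent on that sinus, and the same section also speaks of closing the site.
- **That counting 40 cores as independent units adds to the problem.** That would be a separate issue, present without any bilateral patient, and the plan does not say that cores are the units.

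What the defence does not remove: the exception is not carried into the allocation step or the replacement rule, the second side's assignment is not stated, and the counts fail at b = 1.

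**Conclusion.** The point holds as an inconsistency in unit and counts that should be settled before allocation. The count conflict follows from the documents alone: each bilateral patient either adds one sinus and two cores to the plan or removes one patient from it.

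The statistical consequence depends on which text is followed. Under the sinus rule with independent draws, validity is kept and the loss is partial efficiency. Under whole-patient assignment with a test that ignores the patient, type I error is about 6% to 12% for 2 to 10 bilateral patients. That range rests on an assumed correlation of 0.5 and assumed numbers of bilateral patients. With no bilateral patient, the conflict has no effect, but the plan does not ensure that.

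**What to change.** 1. Make Patient selection, Informed Consent, Pre-operative procedure and Histology / MicroCT assessment agree: the sinus is the unit, 10 per material, 20 sinuses from 20 − b patients, and 40 cores averaged to one value per sinus.
2. In a bilateral patient, randomise which side gets InterOss and give the other side Bio-Oss. Allocate unilateral patients from a balanced list.
3. Add a patient effect to the analysis. The split allocation needs it, because a test that ignores the patient is then conservative: about 3%, 2% and 1% with 4, 6 and 10 bilateral patients.
4. Reconcile Patient Withdrawal and/or Replacement with the sinus as the unit, so that a validly grafted contralateral sinus stays in the analysis when the other site is excluded.

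The cost is protocol wording, a revised allocation list and a slightly more complex model. No patients or procedures are added.
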